 This subject group may require immediate escalation of care and/or hospitalization once the digital monitoring system identifies changes.

Design

During screening, subjects and caregivers will be trained on the CWHMS and assessed for compliance (Table 1-1, panel 1). **Once enrolled,** subjects will receive 2 **complete** cycles of blinatumomab in the outpatient setting in accordance with the monitoring and intervention guidelines (Table 1-1., panels 2 and 3).

After the end of cycle 2 clinical assessment visit, some subjects may continue to receive 2 additional (optional) cycles of **outpatient** blinatumomab. There will be no CWHMS outpatient monitoring during the optional cycles 3 and 4. For the purpose of this study, the MDMP is defined as the first 3 days of cycle 1 (72 hours) and the first 2 days of cycle 2 (48 hours) of blinatumomab infusion for subjects with MRD of B-precursor ALL.

The end of study visit will occur 30 days (+ 3 days) after the last dose of blinatumomab is administered (Figure 1-1).

During the MDMP, the CWHMS will measure vital signs. These vital signs include **pulse** rate, **respiratory rate**, oxygen saturation, **and axillary temperature**. The CWHMS will measure respiratory rate intermittently (sampling every 30 seconds). The subjects will

Date: 21 April 2022 Page 12 of 108

Product: Blinatumomab
Protocol Number: 20190014

take intermittent blood pressure (BP) measurements (using a subject-usable BP device) every 3 hours during the MDMP. The schedule for BP measurements may be extended by HCP (up to but not exceeding every 6 hours) after the first 24 hours of MDMP. The BP device will be provided and will directly transmit the BP reading via the monitoring platform to the **CH Patients Application on the study provisioned mobile phone**.

Threshold vital sign values will be established, and an immediate alert will be generated and transmitted to the **monitoring platform** once the preset threshold values are surpassed and sustained for at least 10 minutes (Table 1-1). **Except for blood pressure**, an alert will be triggered within 1 minute upon being received.

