^c End of Study to be conducted 30 (+3 days) after last dose of blinatumomab

All MRD assessments per institutional standard of care procedures. No central MRD testing will be required Subjects can be transplanted at any time according to institutional guidelines and Standard of Care.

Date: 21 April 2022 Page 19 of 108

Table 1-1. Vital Signs and Clinical Monitoring

AMG 103 20190014 VS and Clinical Monitoring

Panel 1

Education

- HCP, Subjects & Caregivers (CG)
 will receive training in the use
 and functions of the Current
 Health (CH) monitoring
 device(s)(CHDs), including the
 temperature sensor, BP monitor,
 and tablet
- Subject will wear CHDs during screening to establish baseline VS, comfort, and eligibility.
- Subject and CG will be trained to recognize clinical changes/symptoms such as increased lethargy, change in mental status, seizure, jitteriness, fever, fast or difficult breathing and other signs and symptoms
- Subject and CG will be educated on the usual side effects of blinatumomab (IP) infusion.
- Subject and CG will be educated to contact HCP for any change or new finding
- HCPs will be trained on outpatient IP infusion and response algorithm

Panel 2

Monitoring

Electronic monitoring including

- Establishment of Subject baseline during screening
- Remote monitoring of vital signs (VS): Respiratory rate (RR), Pulse rate (PR), temperature(T), Blood Pressure(BP), Oxygen saturation(S).
- Monitoring: Continuous PR, T, and S. intermittent: RR(every 30 secs) and BP(every 3 hrs.)
- HCP may order more frequent VS as needed.
- VS algorithm for ALERT to changes in VS as outlined, which are persistent for ≥ 10 minutes, with the exception of BP, alert will occur within 1 minute of measurement:
 - Systolic BP ≤ 100 mmHg or ≥ 20% reduction from baseline (established in screening)
 - Temp ≥ 38.0°C(100.4°F) (Axillary fever scout ≥37.0°C) (99.4°F))
 - S ≤ 92%
 - $R \le 10 \text{ or } \ge 25$
 - PR \leq 60 or \geq 150
- Neurological algorithm for intervention
 - Any seizure
 - Aphasia (receptive or expressive)
 - Apraxia
 - Altered level of consciousness
 - Impairment of cognitive skills
 - Motor weakness
 - Any change of grade ≥ 3 self-care activities of daily living
 - Any change identified by Patient or caregiver

Panel 3

Intervention

- Subject proximity (≤ 1 hr.) to a advanced medical center
- Pre-dose dexamethasone(20mg) will be given prior to initiation of blinatumomab at every cycle.

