The above benefit risk assessment supports the conduct of this clinical trial. Reference should be made to the Investigator's Brochure for further data on blinatumomab.

Date: 21 April 2022 Page 34 of 108

Training material will be provided by CH with further information on the digital devices used in the study.

3. Objectives and Endpoints

Objectives		Endpoints
Primary		
To determine the safety of blinatumomab administrat MDMP (defined as the first cycle 1 and first 2 days of outpatient blinatumomab in	ion, during the st 3 days of cycle 2 of	 Incidence of grade 3 and/or 4 CRS, NT or any adverse event (AE) requiring hospitalization (SAE) during MDMP.
Secondary		
To determine the time from of grade 3 or 4 vital sign, or clinical change to theraped (any measurable action tall performed on the subject of the clinical parameters deduring the MDMP.	or significant utic intervention ken by or due to onset of	Time (in minutes) from first onset of fever, hypotension, hypoxia, other grade 3 or 4 vital sign including seizure or neurological change (grade 3-limiting self-care activities of daily living [ADL]) to therapeutic intervention ^a
Evaluate the safety and to blinatumomab administers as an outpatient		 Overall incidence and severity of treatment-emergent adverse events (TEAE) and adverse events of interest in particular CRS and NT.
Evaluate the impact of coroutpatient blinatumomab to patient reported outcome health status (GHS), and (QoL).	reatment on (PRO), global	 European Organisation for Research and Treatment of Cancer (EORTC) validated electronic version of QLQ-C30.
Estimate healthcare resou associated with treatment		 TEAEs that resulted in hospitalizations TEAEs that resulted in surgeries. TEAEs that resulted in the use of concomitant medications TEAEs that resulted in the use of device/procedure intervention.

ADL = activities of daily living; AE = adverse event; CG = caregiver; CRS = cytokine release syndrome; EMS = Emergency Medical Service; EORTC = European Organisation for Research and Treatment of Cancer; GHS = global health status; HCP = Health Care Provider; IV = intravenous; MDMP = mandatory device monitoring period; NT = neurotoxicity; PO = by mouth; PRO = patient reported outcomes; QLQ-30 = Quality of Life of Cancer Patients; QoL = quality of life; SAE = serious adverse event; TEAE = treatment-emergent adverse event.

Date: 21 April 2022 Page 35 of 108

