The subject is also provided with a tablet. This tablet allows capture of electronic patient reported outcomes (ePROs), specifically European Organisation for Research and Treatment of Cancer (EORTC) Quality of Life of Cancer Patients (QLQ-C30) for this study (see Section 8.2.8), as well as video calls with their HCP.

The CH platform generates an alert based on pre-specified alarming thresholds. This alert is sent via push notification to a mobile application installed on the **study provisioned** mobile **phone** of the subject's HCP. The HCP can also use this application to review subject vital sign trends and history. A similar application is also provided for access via an internet browser.

In response to an alert, the HCP may schedule (or as needed make) a video call to the subject. (In addition, subject may initiate a call to the HCP if needed). This is via the tablet that the subject is provided and the application installed on the **study provisioned** mobile **phone**. This allows the HCP to immediately and conveniently assess the subject's condition and make an appropriate intervention.

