11.8 Appendix 8. Protocol-specific Definitions

Cytokine Release Syndrome (CRS)

A supraphysiologic response following the administration of blinatumomab therapy that results in the activation or engagement of endogenous or infused T cells and/or other immune effector cells. Symptoms can be progressive, must include fever (\square G1) at the onset, and may include hypotension, capillary leak (hypoxia) and end organ dysfunction.

Table 2 ASTCT CRS Consensus Grading

CRS Parameter	Grade 1	Grade 2	Grade 3	Grade 4
Fever*	Temperature ≥38°C	Temperature ≥38°C	Temperature ≥38°C	Temperature ≥38°C
	•			
Hypotension	None	Not requiring vasopressors	Requiring a vasopressor with or without vasopressin	Requiring multiple vasopressors (excluding vasopressin)
			And/or [†]	
Нурохіа	None	Requiring low-flow nasal cannula [†] or blow-by	Requiring high-flow nasal can- nula [†] , facemask, nonrebreather mask, or Venturi mask	Requiring positive pressure (eg, CPAP, BiPAP, intubation and mechanical ventilation)

Organ toxicities associated with CRS may be graded according to CTCAE v5.0 but they do not influence CRS grading.

Source: Lee et al, 2018.

Fever

Fever as defined in the Common Terminology Criteria for Adverse Events (CTCAE) v5.0 is "a disorder characterized by elevation of the body's temperature above the upper limit of normal (ULN)," and a temperature $\geq 38.0^{\circ}\text{C}$ (100.4°F) (for this study, axillary temperature $\geq 37.0^{\circ}\text{C}$ [99.4°F]) is considered grade 1 fever.

For this study, any temperature $\geq 38.0^{\circ}\text{C}$ (100.4°F) maintained for a minimum of 10 minutes will generate an alert. As this study will rely on the fever scout the equivalent alert values from the fever scout will be set at $\geq 37.0^{\circ}\text{C}$ (99.4°F).

CTCAE v5.0 Fever

1 38.0 - 39.0°C (100.4 - 102.2°F)

2 > 39.0 - 40.0°C (102.3 - 104.0°F)

3 > 40.0°C (> 104.0°F) for ≤ 24 hrs

4 > 40.0°C (> 104.0°F) for > 24 hrs

Elevated Pulse Rate

For this study, a **pulse** rate of \geq 150 beats per minute maintained for a minimum of 10 minutes will be considered severe and generate an alert.

Elevated Respiratory Rate

For this study, an elevated respiratory rate of \geq 25 breaths per minute maintained for a minimum of 10 minutes is considered severe and will generate an alert.

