For the purpose of this study, the mandatory device monitoring period (MDMP) is defined as the first three days of cycle 1 (72 hours) and the first 2 days of cycle 2 (48 hours) of blinatumomab infusion.

Therapeutic Intervention (TI)

Therapeutic intervention is any measurable action taken by the subject or performed on the subject as a result of the onset of the clinical parameters described. Such actions may include:

- Advised subject to go to hospital/ER immediately
- Advised subject to call 911 immediately
- Advised to suspend blinatumomab
- Advised to take antipyretic (e.g. acetaminophen)
- Advised subject to take dexamethasone
- Advised to suspend blinatumomab and take antipyretic
- Advised to suspend blinatumomab and take dexamethasone
- Advised to take other medication

• Other (if Other, describe the intervention)

Time to Therapeutic Intervention (TTI)

Time to therapeutic intervention is the time between the delivery of the device alert or unscheduled contact with HCP by subject/CG to report a change to the time of initiation of the therapeutic intervention.

TTI will be calculated as duration (in minutes) from time of the device alert (alarm triggered) to the time of initiation of the therapeutic intervention (i.e. when HCP silenced the alarm and advised an intervention).

If there is a case where the alarm is triggered, and the HCP advised an intervention, but event is not resolved and subject/CG presses the alarm again then that would be considered as a separate event (as alarm ID will be different) to calculate TTI.

TTI will be calculated for all the valid alarm triggers which leads to an intervention. If the calculated TTI is considered incongruous (i.e. more than 15min.) then a query will be entered in DIIR log.

All the scenarios defined below will be considered as invalid for calculation of TTI:

- If no intervention is required (e.g. technical issues) corresponding to an alarm.
- If intervention time is prior to the time of device alert (alarm triggered).

Treatment-emergent Adverse Event

Treatment-emergent Adverse Event is defined as adverse events starting on or after first dose of blinatumomab as determined by "Did event start before first dose of investigational product" equal to "No" or missing on the Events eCRF and up to the end of study visit.

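### The axillary fever alarm threshold is printed as 37.0°C (99.4°F) in four places, but the two values differ by 0.44°C (0.8°F)

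*Protocol*

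**What the plan says.** The axillary sensor's threshold is printed four times across the two documents, each time as 37.0°C or above with 99.4°F beside it:

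- Protocol Table 1-1, Panel 2 (vital-sign alert algorithm): "Axillary fever scout ≥37.0°C) (99.4°F".
- Protocol Appendix 8, Fever, study definition for axillary readings: the pair ends "99.4°F]) is considered grade 1 fever".
- Protocol Appendix 8, Fever, device setting: "the equivalent alert values from the fever scout will be set at" the same pair. It is presented as the counterpart of 38.0°C (100.4°F), sustained for at least 10 minutes.
- SAP Appendix E, Table 1, Panel 2, which repeats the protocol table.

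Elsewhere the protocol describes thresholds without values. The Synopsis says "Threshold vital sign values will be established, and an immediate alert will be generated", and Section 6.1.2 says "The CH platform generates an alert based on pre-specified alarming thresholds".

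The threshold bears on the key secondary endpoint. Protocol Section 3 defines that as "Time (in minutes) from first onset of fever, hypotension, hypoxia" and other listed changes, up to therapeutic intervention. SAP Section 5 makes this operational: "TTI will be calculated as duration (in minutes) from time of the device alert (alarm triggered") to the start of the intervention. SAP Section 9.6.1 tabulates alarms by reason, and axillary temperature is one of the reasons.

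**The concern.** A threshold given in two units should be one temperature. Here a sustained axillary reading from 37.0°C up to 37.44°C is an alarm under the Celsius figure and not under the Fahrenheit figure. The same holds for the study's grade 1 fever definition: an axillary reading of 37.2°C (98.96°F) is fever in one unit and not in the other.

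The direction of the practical effect depends on which figure was intended and which was entered:

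- **37.0°C intended, 99.4°F entered.** Alarms that the plan wants would not fire. Appendix 8 requires fever at the onset of CRS, and Protocol Section 2.1 relies on the devices to help the healthcare provider recognise developing CRS.
- **99.4°F intended, 37.0°C entered.** Subjects would alarm from 98.6°F. That adds to a monitoring workload which the Amendment 2 rationale already names as a barrier to site participation.

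Either way, the threshold determines which temperature alarms are available to the alarm counts and, where an intervention follows, to the TTI summary.

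**Working it through.** **Inputs.** Axillary pair 37.0°C and 99.4°F (the four places above). Comparison pairs from Protocol Appendix 8: 38.0°C/100.4°F, 39.0°C/102.2°F and 40.0°C/104.0°F, including the CTCAE grade 1 row "38.0 - 39.0°C (100.4 - 102.2°F").

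**Formulas.** F = C × 9/5 + 32 and C = (F − 32) × 5/9.

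**Step 1: reproduce the plan's other conversions.**

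| Celsius | Computed °F | Printed °F |
|---|---|---|
| 38.0 | 100.4 | 100.4 |
| 39.0 | 102.2 | 102.2 |
| 40.0 | 104.0 | 104.0 |

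All three agree. The grade 2 row starts at 102.3°F for temperatures above 39.0°C, which is simply the next tenth of a degree.

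**Step 2: the axillary pair.**

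- 37.0 × 9/5 + 32 = 98.6°F, against 99.4°F printed.
- (99.4 − 32) × 5/9 = 37.44°C, against 37.0°C printed.
- Gap: 99.4 − 98.6 = 0.8°F, or 37.44 − 37.0 = 0.44°C.

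**Step 3: could rounding explain it?** To one decimal, 37.0°C covers 36.95 to 37.05°C, which is 98.51 to 98.69°F. To one decimal, 99.4°F covers 99.35 to 99.45°F, which is 37.42 to 37.47°C. The ranges do not meet; the shortfall is 99.35 − 98.69 = 0.66°F.

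**Step 4: could it be a text-extraction fault?** The same pair occurs four times in two documents, next to conversions that are right. That makes a reading error implausible.

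**Step 5: a possible origin (inference, not stated in the documents).** Subtracting 1 from the standard fever threshold separately in each unit gives both printed figures: 38.0 − 1 = 37.0°C and 100.4 − 1 = 99.4°F. A step of 1°F is only 5/9 = 0.56°C, so the two figures imply different axillary offsets, 1.0°C and 0.56°C. If this is what happened, 99.4°F is not a stray digit, and the text alone does not show which offset was wanted.

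**The case against.** The strongest reply is that this is an editorial slip in a bracketed conversion. Celsius comes first in all four places, and the surrounding definitions are also Celsius-first, so a reader would take 37.0°C as the setting and 99.4 as a misprint for 98.6. The protocol refers device details to an approved device manual outside these documents, and Amendment 2 reports experience with alarms already generated. A threshold was therefore in use, and nothing shows that it was wrong. The analyses are descriptive, with no hypothesis tested. TTI is calculated only for valid alarms that lead to an intervention, and the provider acts on the vital signs together with clinical status, so extra low-grade alarms need not reach the TTI summary. SAP Section 5 also allows TTI to start at an unscheduled contact, although its calculation sentence uses the alarm. Other safeguards exist: data refreshed every 30 seconds, video checks at least every 12 hours, a caregiver in the home throughout the monitoring period, a patient alarm button and an oral thermometer. Both printed values also lie below 38.0°C.

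Most of this stands and limits the consequence. 37.0°C is the more natural reading, the configured value may well be right, and the alarm is one safeguard among several. It does not remove the error. The mismatch sits in the alarm setting and in a study-specific fever definition, and neither document settles which figure applies. The possibility that the external manual holds the correct value is a reason to check it, not to leave the text as it is.

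**Conclusion.** The printed pair is wrong by 0.44°C (0.8°F) in all four places. This is certain arithmetic and rests on no assumption beyond the standard conversion.

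The consequence is limited but real. The threshold governs which axillary alarms fire, hence the alarm counts by reason in SAP Section 9.6.1 and the pool of alarms from which TTIs can arise. It also leaves axillary grade 1 fever with two definitions. It does not alter how a TTI is measured once an alarm has fired, CRS grading (which uses 38°C), the exact binomial interval for the primary endpoint, or the sample size. The effect on the number of alarms or TTIs cannot be estimated, because the documents give neither a distribution of axillary temperatures nor the configured setting. The point should be fixed because a home-monitoring alarm needs one unambiguous value, but it does not threaten the trial's conclusions.

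**What to change.** The sponsor should confirm the intended axillary threshold and correct Protocol Table 1-1, both sentences in Protocol Appendix 8, and SAP Appendix E:

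- If Celsius was intended, print 37.0°C or above (98.6°F).
- If Fahrenheit was intended, print 99.4°F or above (37.4°C, rounded from 37.44°C). Because 37.4°C converts back to 99.32°F, state which unit is entered on the platform.

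In either case, verify the value configured on the monitoring platform against the confirmed threshold.

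A separate, minor clarification can be made at the same time. SAP Section 9.6.4 names axillary temperature among the vital signs but lists only 38.0°C or above as abnormal. If axillary readings from the wearable system feed the abnormal-change table, use the confirmed axillary threshold for them and keep 38.0°C for non-axillary clinic readings.

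The cost of the main correction is a one-line edit in four places and a check of one device setting. No additional data are needed.
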